5.5 Safety variables

5.5.1 Definition of treatment-emergency, baseline and change-from-baseline, last on treatment, follow-up assessments for safety variables

For all safety data analyses described in this SAP, baseline is considered to be the last valid assessment prior to first study drug intake.

For each individual safety variable, baseline is defined to be the last valid measurement available before the date and time of first dose intake of study treatment, unless otherwise specified. On days where study drug is initiated or re-initiated, the pre-dose assessment for that day is defined as the last non-missing assessment prior to the study drug intake on that day. The pre-dose assessment on Day 1 (if available) is identical to baseline; however, missing pre-dose data on Day 1 is not imputed with baseline. In case of (partially) missing assessment dates/times, or for assessments reported on Day 1 (or day of re-initiation) with recorded assessment time contradicting the time point label (e.g., pre-dose, 2 hours post-dose), the nominal visit and time point labels will be used to determine whether an assessment is considered for baseline (for example a blood pressure measurement with an assessment date on Day 1 but with a missing assessment time or an assessment time prior to the reported time of first study drug intake, will not be considered for baseline if reported under the time-point “2 hours post-dose” in the eCRF, however it will be considered if reported as “Pre-dose” in the eCRF).

Absolute changes from baseline are defined as post-baseline value minus baseline value, i.e., a positive sign indicates an increase compared to baseline.

A percentage change from baseline is defined as the absolute change from baseline divided by the baseline value (if the baseline value is > 0) and then multiplied by 100.

Absolute and percent change from baseline is calculated and stored for all continuous safety data.

In addition, the following assessments are flagged or derived per parameter:

- Last on-treatment assessment: Last assessment prior to or on EOT date +1 day)
- Day-15 follow-up, between EOT + 8 days and EOT + 22 days [see Section 11.4]
- Day-30 follow-up, between EOT + 23 days and EOT + 37 days [see Section 11.4]
- Last follow-up assessment: Last assessment between EOT + 8 and EOT + 37 days

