A safety assessment (ECG, vital signs, laboratory) is considered treatment-emergent, if the assessment date is on or after the study treatment start date and prior to or on the study treatment end date + 15 days (inclusive). If both, the assessment date/time and the date/time of study treatment start are available, only events with date/time on or after the date/time of study treatment start are considered to be treatment emergent. In case of (partially) missing assessment dates/times, or for assessments on treatment Day 1 with reported assessment time contradicting the time point label, the nominal visit and time point labels will be used to determine whether an assessment is considered as treatment-emergent or not. For example, a blood pressure measurement with an assessment date on Day 1 but a missing assessment time or an assessment time after the time of first study drug intake, will not be considered treatment emergent if reported under the time-point “Pre-dose” in the eCRF, however it will be considered if reported as “2 hours post-dose” in the eCRF.

A safety event (AE, SAE, Death) is considered treatment-emergent if the onset date/date of occurrence is on or after the study treatment start date and prior to or on the EOT date + 15 days (inclusive). Missing or partially missing onset or occurrence dates are imputed as described in Section 12.3. If both the onset/occurrence date/time and the date/time of study treatment start are available, only events with date/time on or after the date/time of study treatment start are considered to be treatment emergent.

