9.10.6 Pulmonary function tests - Spirometry

The following summary displays are provided by treatment group, all based on the SAF:

- Treatment-emergent FEV1, FVC, FEV1/FVC, %FEV1, and %FVC including absolute and percent change from baseline, as described in Section 5.5.13.1, are summarized, by parameter and visit. Except for 'Baseline', 'Last on treatment', 'Day-15 follow-up' and 'Day-30 follow-up', only treatment-emergent results from nominal scheduled visits are included; premature EOT visit is mapped to a scheduled visit [see Section 11.3]. These are summarized descriptively and mean changes from baseline are also presented graphically with their standard error over time (plots starting with zero change at baseline).
- A scatter plot of all measured treatment-emergent %FEV1 values is provided. Treatment groups are color-coded and linear regression lines (with time as explanatory variable) are drawn per treatment group. These regression lines are to visualize the course over time after an initial change in pulmonary function and for that reason, exclude measurements taken prior to study day 26. The regression equation is given in a footnote.
- Number and percentage of subjects with any occasion of treatment-emergent low spirometry values as defined in Section 5.5.13.1 are presented. Percentages are based on the number of subjects with at least one treatment-emergent result available for the corresponding parameter;

- In the subset of subjects experiencing a decrease of ≥ 200 mL or $\geq 12\%$ in FEV1 (or FVC) from baseline to the last assessment on treatment, the number and percentage of subjects with the condition reversed, not reversed, or missing data on reversibility at the last follow-up result is provided;
- FEV1, FVC, FEV1/FVC, %FEV1, %FVC at the following three time points (for definition, see Section 5.5.1) are displayed graphically by box-and-whisker plots visualizing mean, median, interquartile ranges, SD, and outliers over time: Baseline, last assessment on treatment, and Day-15 follow-up assessment. All subjects with data available at all three time points are included. A corresponding table is included as well.
- Individual absolute change from baseline to last assessment on treatment versus absolute change from baseline to last follow-up assessment is graphically displayed for FEV1, FVC, %FEV1, and %FVC by means of scatterplots with treatment groups color-coded.

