9.10.7 Pulmonary function tests - DL_{CO}

The following summary displays are provided by treatment group, all based on the DL_{CO} sub-study safety analysis set:

- Treatment-emergent Hemoglobin corrected DL_{CO}, Percent predicted DL_{CO}, and DL_{CO} including absolute and percent change from baseline as described in Section 5.5.13.2, are presented, by parameter and visit. Except for 'Baseline', 'Last on treatment', 'Day-15 follow-up' and 'Day-30 follow-up', only treatment-emergent results from nominal scheduled visits are included; premature EOT visit is mapped to a scheduled visit [see Section 11.3]. These are summarized descriptively and mean changes from baseline are also presented graphically with their standard error over time (plots starting with zero change at baseline). The analysis is repeated based DL_{CO} measurements graded acceptable.
- A scatter plot of all measured treatment-emergent Percent predicted DL_{CO} values is provided. Treatment groups are color-coded, and linear regression lines are drawn per treatment group. This regression lines are to visualize the course over time after an initial change in pulmonary function and for that reason, excludes any measurements taken prior to study day 26. The regression equation is given in a footnote.
- Number and percentage of subjects with any occasion of treatment-emergent low Hemoglobin corrected DL_{CO}, Percent predicted DL_{CO}, and DL_{CO} values as defined in Section 5.5.13.2 are presented. Percentages are based on the number of subjects with

at least one treatment-emergent result available for the corresponding parameter. The analysis is repeated based DL_{CO} measurements graded acceptable.

- Hemoglobin corrected DL_{CO}, Percent predicted DL_{CO}, and DL_{CO} at the following three time points [for definition, see Section 5.5.13.2] are displayed graphically by box-and-whisker plots visualizing mean, median, interquartile ranges, SD, and outliers over time: Baseline, last assessment on treatment, and Day-15 follow-up assessment. All subjects with data available at all three time points are included. A corresponding table is included as well.
- Individual absolute change from baseline to last assessment on treatment versus absolute change from baseline to last follow-up assessment is graphically displayed for Hemoglobin corrected DL_{CO}, Percent predicted DL_{CO}, and DL_{CO} by means of scatterplots with treatment groups color-coded.

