2.2. Safety

Condition	Type	Identifier	Source/Instructions	Additional information expected?	Important PD
On Day 1 or on day 1 of re-initiation, any post-dose assessment not performed within 24 hours after pre-dose assessments	M	PD_MM.155	Monitor PD / To be reported in FDM database		Yes
On Day 1 or first day of re-initiation of study drug when post-dose monitoring is required, subject discharged from hospital before 4 hours post-dose or before criteria for discharge were met	M	PD_MM.062	eCRF / Monitor PD / To be reported in FDM database		Yes

	TPL-100062 Protocol Deviation Code List
Protocol Number: AC-058B301 Acronym: OPTIMUM	

Post-dose monitoring not performed according to study protocol on Day 1 or first day of re-initiation of study drug when post-dose monitoring is required	M	PD_MM.063	Monitor PD / To be reported in FDM database	No
During maintenance period, any interruption > 3 days where study drug was re-initiated without up-titration and post-dose cardiac monitoring	M	PD_MM.056	eCRF / Monitor PD	Yes
Study drug not interrupted or discontinued (if applicable) upon subject experiencing an event of suspected opportunistic infection	M	PD_MM.067	eCRF / Monitor PD	Yes
Study drug not interrupted or discontinued (if applicable) upon subject reaching any cardiovascular discontinuation criterion	M	PD_MM.064	Vendor data / Monitor PD	Yes
Study drug not interrupted or discontinued (if applicable) upon subject reaching any hematological abnormalities discontinuation criterion	M	PD_MM.065	Vendor data / Monitor PD / GCS&E input	Yes
Study drug not interrupted or discontinued (if applicable) upon subject reaching any respiratory system (PFT decrease and persistent respiratory AEs) monitoring and discontinuation criterion	M	PD_MM.068	Vendor data / Monitor PD	Yes
Study drug not interrupted or discontinued (if applicable) upon pregnancy determination	M	PD_MM.069	eCRF / Monitor PD	Yes
Study drug not interrupted or discontinued (if applicable) upon subject reaching any liver abnormalities monitoring and discontinuation criterion	M	PD_MM.071	Vendor data / Monitor PD / For CDDM only: to be coded once	Yes
Study drug not interrupted or discontinued (if applicable) upon subject reaching any renal function discontinuation criterion	M	PD_MM.072	Vendor data / Monitor PD	Yes
Study drug not interrupted or discontinued (if applicable) upon subject reaching any ocular abnormalities discontinuation criterion	M	PD_MM.073	eCRF / Monitor PD	Yes

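### The lung-function regression lines run to EOT + 15 days with no subject effect, so the printed slope may understate an on-treatment decline

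*SAP*

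**What the plan says.** Section 9.10.6: "A scatter plot of all measured treatment-emergent %FEV1 values is provided". On it, "linear regression lines (with time as explanatory variable) are drawn per treatment group", and "These regression lines are to visualize the course over time after an initial change in pulmonary function". Values before study day 26 are left out, and the regression equation is printed in a footnote. No standard error, confidence interval or test is planned.

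Section 9.10.7 does the same for the DLCO sub-study: "A scatter plot of all measured treatment-emergent Percent predicted DL_{CO} values is provided", again with one line per arm, the day-26 cut, the same purpose and the equation in a footnote.

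Neither section sets an upper time limit. Section 5.5.1 takes treatment-emergent assessments to be those "prior to or on the study treatment end date + 15 days (inclusive"). It also gives a tighter limit, "Last on-treatment assessment: Last assessment prior to or on EOT date +1 day"), and places follow-up assessments from EOT + 8 days onward.

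The visit tables put lung-function tests at baseline, Weeks 4, 12 and 60, EOT, FU1 and FU2. FU1 is targeted at 15 days after last intake, with a window of -1 to +7 days. The protocol deviation code list refers to a "respiratory system (PFT decrease and persistent respiratory AEs) monitoring and discontinuation criterion", so stopping linked to lung function is possible.

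**The concern.** The lines are meant to show what happens after the early change, and the day-26 cut protects that purpose at the left end of the axis. Nothing protects the right end. A test between EOT + 8 and EOT + 15 days is a follow-up value under Section 5.5.1, and the same SAP uses follow-up values to judge reversibility. Here it also enters the on-treatment line. For completers such values lie at the far right of the time axis, where they pull hardest on a slope.

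The fit is also described with time as the only explanatory variable and raw percentages as the response. If subjects with low values leave earlier, the later points come from a healthier group, and a line through the pooled points reads that change of composition as improvement.

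Both effects push the slope upward, which in a safety display is the direction that hides a decline. Among the planned lung-function outputs, this line is the only one that states a rate of change after the initial drop.

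**Working it through.** The SAP states no slope or precision for these lines, so there is no figure to reproduce.

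**Inputs from the SAP.** 1133 subjects randomized 1:1, about 566 per arm. On-treatment tests from day 26 at days 29, 85, 421 and 757 (Week 4, 12, 60 and 108 targets) or at premature EOT. FU1 window 14 to 22 days after last dose. Of those 9 days only days 14 and 15 fall within EOT + 15, so 2/9 = 22% if visits were spread evenly. The real share is unknown and could be higher, because day 15 is the target.

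**Inputs assumed, not in the SAP.** True on-drug slope -1.0 point/year; off-drug recovery 0 to 8 points; between-subject SD 12 and within-subject SD 4; dropout 0 to 30%.

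**Step 1: pooling alone.** With complete data and no off-drug values, the simulated pooled slope is -0.99 and the within-subject slope is -0.99. Dropout of 15% or 30% unrelated to FEV1 leaves the pooled slope at -1.03 or -1.01. Pooling by itself causes no slope bias.

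**Step 2: off-drug values, no dropout.** Let a share f of subjects have an FU1 test at day 772 that is r points higher. The pooled slope shifts by

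shift = f × r × (u - m) / S,

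where u = 772/365.25 = 2.114 years, m is the mean time over all points and S is the sum of squared deviations of time per subject. The four on-treatment times are 0.079, 0.233, 1.153 and 2.073 years.

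- f = 2/9: m = 0.949, S = 2.87, so r = 4 gives 0.222 × 4 × 1.165 / 2.87 = 0.36 and a slope of -0.64.
- f = 0.5: m = 1.021, S = 3.23, so r = 4 gives 0.5 × 4 × 1.093 / 3.23 = 0.68 and a slope of -0.32.

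The simulation agrees to within its sampling error:

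| Recovery (points) | 22% of FU1 tests | 50% | 100% |
|---|---|---|---|
| 0 | -0.97 | -1.00 | -0.98 |
| 2 | -0.79 | -0.67 | -0.47 |
| 4 | -0.67 | -0.32 | +0.04 |
| 8 | -0.30 | +0.34 | +1.12 |

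Setting the shift to 1.0 in the formula, reversal from this source alone needs a recovery above S / (f × (u - m)). That is about 11 points at 22%, 5.9 at 50% and 3.8 at 100%.

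**Step 3: dropout related to low FEV1.** The premature-EOT test is kept. The log-odds of dropout rise by 0.5 (moderate) or 1.0 (strong) per SD of lower FEV1.

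| Base dropout | Relation | Pooled, no FU1 | Pooled, 22% FU1 and 4-point recovery | Within-subject, on drug, no FU1 |
|---|---|---|---|---|
| 15% | moderate | -0.66 | -0.28 | -1.02 |
| 15% | strong | -0.18 | +0.12 | -1.00 |
| 30% | moderate | -0.38 | -0.01 | -1.02 |
| 30% | strong | +0.20 | +0.54 | -1.02 |

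The third column already contains only on-drug values. An earlier cut-off alone therefore does not remove the dropout effect; a subject effect is also needed. When individual slopes also vary and drive dropout, the within-subject slope is -0.93, so a little bias can remain.

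**The case against.** The strongest reply is that these are lines on a scatter plot. No inference is attached, and the same sections plan other displays: by-visit changes from baseline with separate last-on-treatment and follow-up rows, box plots at baseline, last on-treatment and Day-15 follow-up, individual scatterplots of on-treatment against follow-up change and, for spirometry, a reversibility table. These separate on-drug from off-drug values, so a decline hidden in the line need not be hidden in the report. This stands and limits the weight of the point. It does not remove it, because none of those displays gives a rate of change.

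A second reply is that few FU1 tests fall within EOT + 15 days, and that for early discontinuers they fall mid-axis. This also stands: at a 22% share, even an 8-point recovery left the slope negative.

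A reader might infer that using repeated values without a subject term biases the slope in itself, or that the lines are bound to hide a decline. The documents support neither. Pooling mainly affects precision, and none is reported. Bias needs off-drug recovery or dropout related to lung function, and the SAP gives a size for neither. The code list shows only that a lung-function criterion for interruption or discontinuation exists, not its threshold. That the fit ignores the subject is itself inferred from the absence of any subject term.

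A further gap is that the definition of treatment-emergent assessments in Section 5.5.1 lists ECG, vital signs and laboratory, not lung function. The EOT + 15 limit applies here because Sections 9.10.6 and 9.10.7 use the term without one of their own.

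**Conclusion.** The point holds as a conditional one. The lines use values that the SAP itself classes as follow-up, and they name no subject effect, so the printed slopes may understate an on-treatment decline. Under the assumptions above, a true -1.0 point/year is attenuated to about -0.67 or -0.32 by a 4-point recovery with 22% or 50% of FU1 tests included, and to about -0.66 or -0.18 by 15% dropout moderately or strongly related to low FEV1. Reversal needs marked recovery in a large share of subjects, strong outcome-related dropout, or both together. With neither mechanism the slope is unbiased. The consequence is limited to a descriptive safety display.

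**What to change.** In Sections 9.10.6 and 9.10.7:

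- Fit the line only to values from study day 26 to EOT + 1 day, the SAP's own on-treatment limit. Later values can stay on the plot with a different symbol.
- Estimate the line with the continuous-time mixed model with random subject intercept in Section 10.3.2, adding the baseline value as covariate, and print that slope in the footnote.
- State the time window for lung-function assessments explicitly, since the definition in Section 5.5.1 does not name them.

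The cost is a few lines of SAP text and code that is largely written; no new data are needed. The downside is that slightly fewer values enter the line, including some EOT-visit tests done more than 1 day after the last dose.

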9.10.7 Pulmonary function tests - DL_{CO}

The following summary displays are provided by treatment group, all based on the DL_{CO} sub-study safety analysis set:

- Treatment-emergent Hemoglobin corrected DL_{CO}, Percent predicted DL_{CO}, and DL_{CO} including absolute and percent change from baseline as described in Section 5.5.13.2, are presented, by parameter and visit. Except for 'Baseline', 'Last on treatment', 'Day-15 follow-up' and 'Day-30 follow-up', only treatment-emergent results from nominal scheduled visits are included; premature EOT visit is mapped to a scheduled visit [see Section 11.3]. These are summarized descriptively and mean changes from baseline are also presented graphically with their standard error over time (plots starting with zero change at baseline). The analysis is repeated based DL_{CO} measurements graded acceptable.
- A scatter plot of all measured treatment-emergent Percent predicted DL_{CO} values is provided. Treatment groups are color-coded, and linear regression lines are drawn per treatment group. This regression lines are to visualize the course over time after an initial change in pulmonary function and for that reason, excludes any measurements taken prior to study day 26. The regression equation is given in a footnote.
- Number and percentage of subjects with any occasion of treatment-emergent low Hemoglobin corrected DL_{CO}, Percent predicted DL_{CO}, and DL_{CO} values as defined in Section 5.5.13.2 are presented. Percentages are based on the number of subjects with

at least one treatment-emergent result available for the corresponding parameter. The analysis is repeated based DL_{CO} measurements graded acceptable.

- Hemoglobin corrected DL_{CO}, Percent predicted DL_{CO}, and DL_{CO} at the following three time points [for definition, see Section 5.5.13.2] are displayed graphically by box-and-whisker plots visualizing mean, median, interquartile ranges, SD, and outliers over time: Baseline, last assessment on treatment, and Day-15 follow-up assessment. All subjects with data available at all three time points are included. A corresponding table is included as well.
- Individual absolute change from baseline to last assessment on treatment versus absolute change from baseline to last follow-up assessment is graphically displayed for Hemoglobin corrected DL_{CO}, Percent predicted DL_{CO}, and DL_{CO} by means of scatterplots with treatment groups color-coded.

All DL_{CO} results (derived mean values per assessment) are listed by treatment group and visit based on the SCR.

9.10.8 Analysis of other safety variables

Other safety assessment results will be listed. This comprises the following assessments: Dermatological examination, OCT, and Ophthalmological Examination and Columbia Suicide Severity assessment.

9.10.8.1 Columbia Suicide ideation or behavior

Suicidal Ideation, Suicidal Behavior or Self-Injurious Behavior without Suicidal Intent will be listed for each patient, at each assessment visit on the SAF. Events occurring during the period up to EOT + 15 days (treatment-emergent period) will be flagged.

Number (%) of subjects with suicidal ideation (overall and by category), suicidal behavior (overall and by category), suicidal ideation score ≥ 4 or suicidal behavior and/or self-injurious behavior without suicidal intent will be tabulated by treatment group and visit, as well as up to EOT + 15 days (worst outcome). Analyses will be based on subjects in the SAF who have at least one eC-SSRS measurement during the respective visit or period available. The analysis will be repeated in the subgroup of patients with no baseline result available.

For subjects who have in addition a baseline eC-SSRS assessment available shifts from baseline (maximum score from pre-treatment recent history) to the worst reported outcome (the maximum score) up to EOT + 15 days will be tabulated by treatment group to demonstrate any changes in Suicidal Ideation and Suicidal Behavior score categories.

9.11 Analysis of quality of life variables

9.11.1 Change from baseline by visit up to Week 108 in SF-36v2™ Health Survey domain and component scores

Quality of life analysis based on the SF-36v2™ will be performed on the FAS.

The eight normative (t-scores) domain scores, PCS and MCS will be summarized descriptively over time (Baseline, Weeks 12, 24, 60, 84, 108) by treatment groups (observed and LOCF). Changes overtime will be graphically presented for each of the domains, PCS and MCS by treatment group (mean and \pm SE). The health transition item (#2) will be summarized separately (in categories) by visit and a shift table from baseline to Week 108 (observed and LOCF) will be prepared.

